### 4.2.2 Secondary Outcome Measures

#### Objective 2a: To evaluate for whom the FN delivery strategy is most effective

Related secondary outcome measures include retention in services and satisfaction with FN

- Retention in services will be defined as ≥4 visits within 90 days after randomization, or resolution of service need, for children receiving psychotherapeutic or psychopharmacological services.
- Satisfaction with Hospital Care Questionnaire (HCQ). The SHCQ addresses aspects of care including information, patient autonomy, and emotional support.
- Interpersonal Relationship with Navigator (PSN-I) is a validated 9-item scale with strong psychometric properties in samples of culturally diverse, underserved patients.
- Qualitative Parent Interviews: We will explore how cultural and linguistic concordance affects family engagement with mental health services and achievement of families' service goals. We will address this question qualitatively through hour long interviews with families about their experiences and perspectives working with a FP. We will purposively sample families for whom there was and was not cultural and/or linguistic concordance with the FP. These interviews are optional. Parents will have the option to consent to the qualitative interview at the time of enrollment. Parents may choose not to participate in the interview and still participate in the study. Families who agree to the qualitative interview will be contacted by our research staff at 6 months to schedule the interview. The interview will be done via BMC Zoom but will be audio recorded with a separate audio recording device. We will

conduct interviews in English, Spanish, and Vietnamese. Vietnamese interviews will be done using a phone interpreter who will interpret the questions and answers. After families complete the interviews they will receive a \$20 Clincard to thank them for their time.

- **Qualitative DotHouse Staff Interviews:** We will interview different DotHouse clinic staff ( providers, nurses, case managers, etc) to gather their perspective on the implementation of Family Navigation. These interviews will last approximately 30-40 minutes and will gather information on work flow changes for example. We will gain an understanding of the implementation of FN in a clinic setting. We will present the opportunity for these interviews during the clinic's all staff meetings and will contact providers by email to invite them to participate to the study. We will attach an exempt information sheet to the email. We will schedule interviews with interested providers and obtain verbal permission to participate and be audio recorded. Interviews will be done exclusively in English.

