**Table 1. Primary and Secondary Outcomes**

	Outcome	Description	Measurement Source	Timing
Primary	Time to services	Time from randomization to first behavioral health service encounter	Electronic health record including FP's template documentation	90 days
	Access to services	1 st encounter with behavioral health services within 90 days of randomization	Electronic health record including FP's template documentation	90 days
	Child symptoms	Score on PSC-17 and SWYC	Measures will be sent to families via Epic's mobile app MyChart or administered by Zoom/telephone in REDCap or sent to the parent by mail	Baseline 3, 6, 9, & 12 mo
Secondary	Retention in services	≥4 visits or resolution of service need for families receiving psychotherapeutic or psychopharmacological services	Electronic health record including FP's template documentation	90 days
	Patient Satisfaction	HCQ & PSN-I	Measures will be sent to families via Epic's mobile app MyChart or administered by Zoom/ telephone in REDCap or sent by mail	6 mo
	Qualitative Parent Interviews	Parent interviews to describe the effect of cultural and linguistic concordance between patients and FN.	Interview completed through Zoom/phone and audio recorded, stored in HIPPA compliant BOX drive.	6 mo
	Qualitative DotHouse Staff Interviews	DotHouse staff interviews to understand their perspective in the implementation of family navigation (work flow changes etc).	Interview completed through Zoom/phone and audio recorded, stored in HIPPA compliant BOX drive.	ongoing

Note: The PSC-17 is currently administered to children at pediatric well visits at DotHouse as part of usual care. Plans are to implement the SWYC in summer/fall of 2018. Both tools have been used extensively and research supports use for symptom monitoring.

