**Strategy C: Pediatric Surveillance v. Enhanced: Tracking at 3, 6, 9, and 12 months.** In core FN (i.e. Pediatric Surveillance at well-child visits), monitoring is determined by standard pediatric practice. In Massachusetts, behavioral screening is mandated at every pediatric visit, which for children in the target population (ages 3-12 years) is annually. In experimental conditions with "enhanced monitoring," FPs will screen children using validated instruments quarterly (SWYC, PSC-17 based on age) and communicate results to the child's care team. The screening tools will be deployed through MyChart , the EPIC EHR patient portal. Results feed directly into the child's record. Screening tools may also be deployed through REDCap or mailed to the parent in a sealed envelope with a stamped and addressed return envelope inside. Once the mailed parent measures are received by research staff at Boston Medical Center, they will be manually entered into RedCap and the paper copies will be stored in a locked filing cabinet in a locked office. The FP will be responsible for initiating and tracking the screening. She will message the child's PCP when new screening results are available and communicate with the PCP and care team regarding any changes in symptoms. We expect additional costs of increased monitoring to be modest, and that the additional information will allow care to be better aligned with children's symptomatology and, thus, lead to improved engagement with services.

**Strategy D: tailored vs standardized, schedule-based visits with families.** Families who receive tailored visits, will work with their FN on addressing issues as they arise. They will not have any pre-specified schedule for visits or contacts. Families who received standardized scheduled visits, will have a pre-specified schedule of visits. This will include monthly contacts with families for 6 months. Each contact will have a specified agenda which includes review of family goals, and a topic (e.g. what is an individualized education plan) to review.

Regardless of the combination of delivery components to which families are randomized (core or enhanced strategies), families will core FN elements.

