## 11.2 Source Documents

This study includes data collection and management tools that also meet HIPAA security rules to protect confidentiality and security of protected health information.

**Electronic Health Record (EHR):** Data will be abstracted from the EHR of children including diagnoses (from the child's problem list), basic demographic data, and information on scheduled appointments, missed appointments, screening tools administered, screening results, referrals made, referrals completed, billing codes, and surveys collected through MyChart, the EHR's patient portal. MyChart is an interactive system integrated into the patient EHR (Epic/ OCHIN) and offers patients personalized and secure on-line access to portions of their medical records and also allows providers to send messages and to communicate with patients. MyChart will be used to communicate with families, conduct screening, and monitor symptoms, and track study outcomes / measures. Epic/OCHIN is a fully encrypted, HIPAA compliant system. EHR records at the health center are further protected by firewall

technology. The study investigators will only receive de-identified, ID coded MyChart collected data from DotHouse.

All data will be provided by DotHouse to the study investigators in ID coded form.

FP visit templates: FPs will document in the EHR the details of the eight tasks outlined in protocol manuals: 1) initial encounter, 2) assessment of barriers, 3) plan to address barriers, 4) referrals to service (type and location) 5) confirming appointments scheduled, 6) confirming appointments attended, 7) post-assessment follow-up, and 8) connecting with treatment services. De-identified logs will be scored by study staff to measure the number and nature of completed tasks by the FP.

BACO billing data: We will triangulate BACO billing data with EHR data documenting service use. BACO data will allow us to capture behavioral health services provided outside of DotHouse. BACO billing data will be de-identified by staff at DotHouse who are responsible for maintaining the cross walk between patient name and study ID.

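### Retention counts resolved need as success from a source that includes the unblinded Family Partner's notes, and the scheduled chance to learn of resolution differs by factor D

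*Combined protocol and SAP*

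**What the plan says.** Section 4.2.2 gives the secondary outcome: "Retention in services will be defined as ≥4 visits within 90 days after randomization, or resolution of service need". Table 1 repeats it as "≥4 visits or resolution of service need for families receiving psychotherapeutic or psychopharmacological services", measured at 90 days, with the source "Electronic health record including FP's template documentation". Appendix A carries the same two-part definition in a single row for all families. Either part is enough to be scored as retained.

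Section 8, Strategy D, sets out the two visit structures. For standardized visits: "This will include monthly contacts with families for 6 months", and "Each contact will have a specified agenda which includes review of family goals". For tailored visits: "They will not have any pre-specified schedule for visits or contacts".

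Section 11.2 lists eight tasks that the Family Partner documents, ending with "7) post-assessment follow-up, and 8) connecting with treatment services". None of the eight is a rating that the need has been resolved. Under Randomization Procedures in section 9, the Family Partner runs the assignment program, and section 8 has the Family Partner deliver the assigned strategy.

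**The concern.** The two parts of the definition differ in kind. Four visits can be counted from dated records. Resolution is a judgement, and the visible text does not define it, name who makes it, or mask that person. One named source is the notes of someone who knows the assignment, and how often that person is scheduled to ask about goals is what factor D randomizes.

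Take two children with the same course: two visits, then the need met by day 60. In the standardized level, a month-2 or month-3 contact gives the Family Partner a set occasion to hear this and note it. In the tailored level, the occasion depends on whether contact happens to take place. The first child may be scored as retained and the second as not retained.

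The retention contrast for D could then partly reflect how often resolution was asked about and written down. A single combined figure would not show whether a difference came from visits or from recorded resolution.

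**Working it through.** **The plan's own figure.** The only sample size in section 12.2 concerns receipt of services within 90 days: 60% v 75%, two-sided 5%. With 80% power (assumed, because section 12.2 states 80% only for mediation) and pooled variance under the null, the formula gives 151.9, rounded up to 152 per factor level, or 304 in total. This matches the plan. It concerns access; the plan gives no rate or power for retention.

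**What covers the resolution part.**
- Billing data (11.2) are set against record data on service use. They can confirm visits, not that a need was met.
- The blinded research assistant (section 9) administers questionnaires. Retention is not among them.
- The sensitivity analysis in 12.3 treats missing record data as failure to engage. An unrecorded resolution is already scored as not retained, so this would leave unequal recording in place.
- Study staff score de-identified Family Partner logs (11.2), but for completed tasks, and masking is not stated.

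**Illustrative size.** Let v be the proportion with at least 4 visits, r the proportion of the rest whose need truly resolves by day 90, and s1 and s0 the proportions of those resolutions that are recorded under standardized and tailored visits. With v and r equal in both levels (no true effect):

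retention at a level = v + (1 − v) × r × s

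false difference = (1 − v) × r × (s1 − s0)

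None of v, r, s1 or s0 is in the documents; all are assumptions. For n, retention applies to children receiving services. If 67.5% do so (the mean of 60% and 75%), n = 152 × 0.675 ≈ 103 per level.

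Worked case, v = 0.40, r = 0.20, s1 = 0.90, s0 = 0.50:
- standardized: 0.40 + 0.60 × 0.20 × 0.90 = 50.8%
- tailored: 0.40 + 0.60 × 0.20 × 0.50 = 46.0%
- difference: 4.8 points
- standard error: √[(0.508 × 0.492 + 0.460 × 0.540)/103] = 0.0696, so difference/SE = 0.690
- chance that a two-sided 5% test rejects: Φ(0.690 − 1.96) + Φ(−0.690 − 1.96) = 10.6%

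| v | r | s1 v s0 | False difference (points) | Two-sided rejection, n = 103 |
|---|---|---|---|---|
| 0.60 | 0.10 | 0.90 v 0.70 | 0.8 | 5.2% |
| 0.40 | 0.10 | 0.90 v 0.50 | 2.4 | 6.4% |
| 0.40 | 0.20 | 0.80 v 0.60 | 2.4 | 6.4% |
| 0.40 | 0.20 | 0.90 v 0.50 | 4.8 | 10.6% |
| 0.40 | 0.30 | 0.90 v 0.50 | 7.2 | 18.0% |
| any | any | equal | 0 | 5.0% |

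With all 152 per level, the 4.8-point case rejects 13.4% of the time and the 7.2-point case 24.3%. Over v 0.4 to 0.6, r 0.1 to 0.3 and a recording gap of 0.2 to 0.4, the false difference runs from 0.8 to 7.2 points.

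**The case against.** The strongest reply is that tailored families are not left unasked. Section 8 makes goal monitoring part of core navigation for everyone and continues active navigation until the Family Plan goals are met, so the Family Partner must judge goal achievement at both levels of D. Section 5 includes goal monitoring among the components rated for fidelity. This stands: a reader might infer that goals are reviewed at one level only, and the documents do not support that. What differs is the schedule. Core monitoring has no stated interval, while standardized families have about three set reviews by day 90.

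Second, no section says that a goal review produces a resolution entry. Family goals may concern school accommodations or benefits rather than the treatment need. The source is the whole health record, and the protocol manuals, which are not part of the documents, may hold a rule. This also stands: the link is an inference, drawn because the visible text does not say how resolution is established.

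Third, the direction is open. Monthly contact can also bring new or unmet needs to light and so lower recorded resolution. That is possible, though more occasions to learn that a need was met more naturally raise recording than lower it.

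Fourth, resolution with fewer than 4 visits has to occur within 90 days of randomization, a window that includes the wait for a first appointment. True resolution may therefore be uncommon, and the effect small.

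**Conclusion.** The point holds as a risk of unequal ascertainment in one part of a secondary outcome. The definition, its source and the unequal scheduling are all in the text, and no described check covers the resolution part. A bias of known size or direction is not shown. The 0.8 to 7.2 points rest wholly on assumed visit, resolution and recording rates; at the low end the test stays near its nominal 5%, and with equal recording there is no bias.

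A reader might also infer that scheduled visits could enter the optimized package because of this artefact. The documents do not support that: the objectives in sections 2 and 4.1 tie the choice of strategies to access, which this part of the retention definition does not touch. The sample size of 304 is likewise unaffected. What is at stake is the reading of the retention contrast for factor D. Because the correction is cheap and uses data largely collected already, it is worth making.

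**What to change.** In sections 4.2.2 and 12.3 and in Table 1:

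1. Report the two parts of retention separately by factor, alongside the composite.
2. Prespecify the visit part alone (at least 4 visits) as a sensitivity analysis, using dates from the health record and BACO billing. Flag visits known only from Family Partner notes, since section 4.2.1 relies on those notes for dates of services outside DotHouse.
3. For resolution, require the treating clinician's documentation that treatment was completed or the need met. Exclude administrative closure for non-attendance, which would otherwise score a dropout as retained.
4. Have existing study staff who do not see the assigned condition code resolution by the same rule in all conditions.
5. Show resolution known only from Family Partner notes as a separate category, so that information on outside services is kept but does not drive the stricter result.

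The cost is revised outcome wording and a short chart abstraction, mainly for children with services but fewer than 4 visits. No added participants or family contacts are needed. The downside is small: some true resolutions, mainly outside DotHouse, will not count in the stricter version.

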**Table 1. Primary and Secondary Outcomes**

	Outcome	Description	Measurement Source	Timing
Primary	Time to services	Time from randomization to first behavioral health service encounter	Electronic health record including FP's template documentation	90 days
	Access to services	1 st encounter with behavioral health services within 90 days of randomization	Electronic health record including FP's template documentation	90 days
	Child symptoms	Score on PSC-17 and SWYC	Measures will be sent to families via Epic's mobile app MyChart or administered by Zoom/telephone in REDCap or sent to the parent by mail	Baseline 3, 6, 9, & 12 mo
Secondary	Retention in services	≥4 visits or resolution of service need for families receiving psychotherapeutic or psychopharmacological services	Electronic health record including FP's template documentation	90 days
	Patient Satisfaction	HCQ & PSN-I	Measures will be sent to families via Epic's mobile app MyChart or administered by Zoom/ telephone in REDCap or sent by mail	6 mo
	Qualitative Parent Interviews	Parent interviews to describe the effect of cultural and linguistic concordance between patients and FN.	Interview completed through Zoom/phone and audio recorded, stored in HIPPA compliant BOX drive.	6 mo
	Qualitative DotHouse Staff Interviews	DotHouse staff interviews to understand their perspective in the implementation of family navigation (work flow changes etc).	Interview completed through Zoom/phone and audio recorded, stored in HIPPA compliant BOX drive.	ongoing

Note: The PSC-17 is currently administered to children at pediatric well visits at DotHouse as part of usual care. Plans are to implement the SWYC in summer/fall of 2018. Both tools have been used extensively and research supports use for symptom monitoring.

**Objective 2b. To evaluate the mechanisms of FN effectiveness (assessment of mediators and moderators):**

Consistent with a pragmatic design, we will use brief measures that align with standard clinical processes. Measures include:

**Improve Parent Capacity:**

- The Parental Attitudes Towards Psychological Services Inventory—21-item validated questionnaire to assess help-seeking attitudes, help-seeking intentions, and mental health stigma. We hypothesize FN will improve attitudes and reduce stigma, leading to improved *parent capacity* to pursue services.
- Patient Health Questionnaire-2 (PHQ-2)—validated 2-question depression screening tool. We hypothesize that FPs will improve parent mental health by providing support and connection to resources, in turn improving *parent capacity*.

**Increase Access to Resources:**

- Family Resource Scale (FRS)—30-item scale assesses family concerns regarding adequacy of resources. We hypothesize that FN will improve *access to resources* over time.

**Overcome Structural Barriers:**

- Professional contact data. Using FN logs on contacts with others on the care team we will measure level of care coordination (number and frequency of contacts between care providers) and existence of barriers (as delineated in logs). We hypothesize that care coordination by the FP will mitigate structural barriers.

**Table 2. Theory-based Mechanisms and Measures**

Domain	Target	Theoretical	Instrument	Description	Timing
Person	Parent capacity	Improved parental attitudes about mental health increases capacity to engage in services	Parental Attitudes Towards Psychological Services Inventory	26-item questionnaire to assesses mental health attitudes and stigma	Baseline, 6, 12 months
	Parent capacity	Improved parent mental health increases capacity to engage in services	Patient Health Questionnaire-2	Validated 2-question depression screener	Baseline, 3, 6, 9, 12 months
Systems	Access to resources	Improving social determinants increases access to resources	Family Resource Scale	30 items assess adequacy of resources	Baseline, 6, 12 months
	Overcome barriers	Coordination decreases structural barriers	Electronic Health Record FP Templates	Contains resource use and care coordination activities	Monthly data reports

## 5. Study Design

**Type of study design.** Our design is a factorial experiment utilizing a multiphase optimization strategy (MOST). We will test the effectiveness of 4 FN delivery strategies using a randomized (2x2x2x2) full factorial design.

**Study population and setting.** This study will be conducted at DotHouse Health (DotHouse), a federally qualified community health center in one of Boston's most diverse neighborhoods. DotHouse serves >3,000 children in our target age range, of which >85% are racial/ethnic minority and report incomes ≤200% of the federal poverty level. In addition to medical services, the health center provides comprehensive child behavioral health services. Multilingual, multicultural social workers, licensed mental health clinicians, and a psychiatrist provide behavioral care in an onsite behavioral health department, behavioral health clinicians integrated within the pediatric primary care clinic provide assessment and brief intervention. DotHouse participates in Boston HealthNet, an integrated safety-net care delivery system that includes 13 health centers and Boston Medical Center, which provides primary and specialty care in Boston's urban, low income neighborhoods. In 2018, Boston HealthNet will become part of Boston Accountable Care Organization, a model of care designed to address the "triple aim" of improving patient experience, health, and reducing cost.

**Rationale for study design and features.** Specifically, we will use *Multiphase Optimization Strategy (MOST)*, a research method borrowed from the field of engineering, which relies on a randomized, multi-factorial design, and therefore facilitates our ability to simultaneously test the effectiveness of three novel strategies and combinations for delivering FN components. The design will also allow us to test varying combinations of FN factors, ranging from what we propose is the least innovative (core FN) to the most innovative (enhanced technology +community visits +enhanced monitoring). We will then evaluate which combinations of factors are most effective and efficient in regards to achieving the primary outcome (engagement in child mental health services). *This is also a pragmatic experiment.* Similar to pragmatic trials, FN will be integrated into routine clinic workflow and supported by standardized visit templates within the electronic health record which will assist with studying implementation and next steps for dissemination into other primary care and community health centers in the future.

